5. SUBJECT ENROLLMENT

Before subjects begin participation in any study-specific activities/procedures, Amgen requires a copy of the site's written Institutional Review Board/Independent Ethics Committee (IRB/IEC) approval of the protocol, informed consent form (ICF), and all other subject information and/or recruitment material, if applicable (see [Section 11.2](#)). All subjects must personally sign and date the ICF before commencement of study-specific activities/procedures. After meeting all eligibility criteria, a subject is considered enrolled on day 1 (cycle 1 day 1) when the cIV infusion with investigational product is started. The investigator is to document this decision and date in the subject's medical record and in/on the enrollment electronic case report form (eCRF). Adverse events are to be collected for an eligible subject once they are enrolled in the study (from cycle 1 day 1 onwards). Adverse Events occurring during the screening period and which are not related to study procedures will be captured as medical history.

Each subject who enters into the screening period for the study (defined as the point at which the subject signs the informed consent) receives a unique subject identification number before any study procedures are performed. The subject identification number will be assigned manually. This number will be used to identify the subject throughout the clinical study and must be used on all study documentation related to that subject.

PPD

The subject identification number must remain constant throughout the entire clinical study; it must not be changed after initial assignment, including if a subject is rescreened.

All screening tests and procedures should be performed within 21 days before enrollment, unless otherwise noted. All blood and urine samples collected for the

screening assessment (except for biomarkers and soluble CEA [sCEA]) will be submitted and analyzed by the local laboratory. Laboratory assessments used to determine subject eligibility may be repeated once for confirmation (up to a total of 2 times during the screening period), if necessary before the subject is considered a screen failure.

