9.2 Reporting of Adverse Events

9.2.1 Reporting Procedures for Adverse Events That do not Meet Serious Criteria

The investigator is responsible for ensuring that all adverse events observed by the investigator or reported by the subject that occur after the first dose of investigational product through the EOS are reported using the applicable eCRF (eg, Adverse Event Summary).

The investigator must assign the following adverse event attributes:

- Adverse event diagnosis or syndrome(s), if known (if not known, signs or symptoms),
- Dates of onset and resolution (if resolved),

- Severity (and/or toxicity per protocol),
- Assessment of relatedness to investigational product, medical devices, or other protocol-required therapy, and
- Action taken.

If the severity of an adverse event changes from the date of onset to the date of resolution, record as a single event with the worst severity on the Adverse Event Summary eCRF.

The adverse event grading scale used will be the CTCAE, version 4.0. The grading scale used in this study is described in [Appendix A](#). The investigator must assess whether the adverse event is possibly related to the investigational product, medical device(s), and/or other protocol-required therapies. This relationship is indicated by a “yes” or “no” response to the question: Is there a reasonable possibility that the event may have been caused by the investigational product, medical device(s), and/or other protocol-required therapies?

The investigator must assess whether the adverse event is possibly related to any study mandated activity (eg, administration of investigational product, protocol-required therapies, device(s) and/or procedure (including any screening procedure[s])). This relationship is indicated by a “yes” or “no” response to the question: Is there a reasonable possibility that the event may have been caused by a study activity (eg, administration of investigational product)?

The investigator is expected to follow reported adverse events until stabilization or reversibility.

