9.2.2 Reporting Procedures for Serious Adverse Events

The investigator is responsible for ensuring that all serious adverse events observed by the investigator or reported by the subject that occur after signing of the informed consent through 30 days after the last dose of investigational product or the EOS visit (whichever is later) are recorded in the subject’s medical record and are submitted to Amgen. All serious adverse events must be submitted to Amgen within 24 hours following the investigator’s knowledge of the event via the applicable eCRF.

After the protocol-required reporting period defined above, the investigator does not need to actively monitor subjects for serious adverse events. However, if the investigator becomes aware of a serious adverse event after this protocol-required reporting period, the investigator will report the event to Amgen within 24 hours of the

investigator's knowledge of the event. Serious adverse events reported outside of the protocol-required reporting period will be captured within the safety database as clinical trial cases for the purposes of expedited reporting.

The serious adverse event must be submitted to Amgen within 24 hours following the investigator's knowledge of the event via the applicable CRF. If the electronic data capture (EDC) system is unavailable to the site staff to report the serious adverse event, the information is to be reported to Amgen via an electronic Serious Adverse Event (eSAE) Contingency Report Form within 24 hours of the investigator's knowledge of the event. See [Appendix B](#) for a sample of the eSAE Contingency Reporting Form. For EDC studies where the first notification of a Serious Adverse Event is reported to Amgen via the eSAE Contingency Report Form, the data must be entered into the EDC system when the system is again available.

The investigator must assess whether the serious adverse event is possibly related to the investigational product. This relationship is indicated by a "yes" or "no" response to the question: Is there a reasonable possibility that the event may have been caused by the investigational product?

The investigator must assess whether the serious adverse event is possibly related to any study mandated activity or procedure. This relationship is indicated by a "yes" or "no" response to the question: Is there a reasonable possibility that the event may have been caused by a study activity/procedure?

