Appendix B. Electronic Serious Adverse Event Contingency Form

Completion Instructions

Electronic Serious Adverse Event (eSAE) Contingency Reporting Form (for use for Studies using Electronic Data Capture (EDC))

Note, this form is to be used under restricted conditions outlined on page 1 of the form. If you must fax an event report to Amgen, do not enter that event into the EDC system (eg, Rave) unless directed to do so by Amgen.

Header Information

Complete either Section A or Section B and follow the instructions provided within the applicable section.

Section A:

Complete this section and complete only page 1 of the SAE Report Form if the EDC system (eg, Rave) is active and your site does not have access for reasons such as: internet connectivity issues, the EDC system is down, etc.

Section B:

Complete this section and complete all pages of the SAE Report Form if:

- You are submitting a screening serious adverse event report and the database is not active yet
- You are submitting a serious adverse event report and your site access has been removed

1. Site Information

Site Number – Enter your assigned site number for this study

Investigator, Country, Reporter, Phone No., and Fax No. – Enter information requested

2. Subject Information

Subject ID Number – Enter the entire number assigned to the subject

Date of Birth, Sex, and Race – Enter the subject's demographic information

End of Study date – If the subject has already completed the study or terminated the study early, enter the End of Study date

If you are submitting follow-up information to a previous report, provide the adverse event term for the previous report as well as the start date for the initial event.

3. Serious Adverse Event

Provide the date the Investigator became aware of this Serious Adverse Event Information

Serious Adverse Event Diagnosis or Syndrome –

- If the diagnosis is known, it should be entered. Do not list all signs/symptoms if they are included in the diagnosis.
- If a diagnosis is not known, the relevant signs/symptoms meeting serious criteria should be entered.
- If the event is fatal, the cause of death should be entered and autopsy results should be submitted, when available.

Date Started* – Enter date the adverse event first started; not when the event met serious criteria, when a diagnosis was made or when the subject was hospitalized. **This is a mandatory field.**

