Percent change from Baseline is the arithmetic difference between post-Baseline and Baseline divided by Baseline values times 100.

Progression-Free Survival Time

Progression-free survival time is calculated as the number of days from the first administration of AMG 211 to the first assessment of disease progression as per modified irRC or clinical progression, whichever occurs first or death due to any cause, or if applicable date of censoring (date of progressive disease or death or censoring – date of study day 1 +1). Progression-free Survival Time will incorporate the independent radiologic review and/or the Investigator-reported assessment. The progression-free rate at 6 months is defined as the proportion of subjects with no disease or clinical progression at 6 months from the first administration of AMG 211.

The following censoring strategies for missing assessment dates will be used for the progression free survival analysis:

If a subject's disease has not progressed and the subject is alive, progression-free survival time will be censored at the last date they are known to be progression-free (ie, the last evaluable radiological assessment date).

If a subject has no tumor evaluation in the study, progression-free survival time will be censored at the date of the first administration of AMG 211.

Subjects who withdraw consent to participate in the study prior to disease progression will be censored at their last evaluable radiological assessment date.

Screened

A subject is considered in screening once a consent form has been signed.

Study Day

Post study day 1: study day= (date - date of Study Day 1) + 1

Pre study day 1: study day= (date – date of Study Day 1)

Study Day 1

Study day 1 is defined as the first day of administration of the investigational product after enrollment. The day prior to Study Day 1 is considered Day -1.

Treatment-Emergent Adverse Event (TEAE)

A treatment-emergent adverse event is any adverse event starting on or after the first dose of investigational product, as determined by the flag indicating if the adverse event started prior to the first dose on the Adverse Events Summary CRF, and up to and including 30 days after the end of investigational product.

Treatment-Related AE

A treatment-related AE is any treatment-emergent AE that per investigator review has a reasonable possibility of being caused by the investigational product.

Time to Progression (TTP)

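### The SAP's TEAE definition has no clause for worsening, so an event already recorded as an adverse event before first dose can worsen on AMG 211 without entering the TEAE or treatment-related incidence

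*SAP*

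**What the plan says.** SAP section 6 gives the only working definition: "any adverse event starting on or after the first dose of investigational product, as determined by the flag indicating if the adverse event started prior". Status is thus settled by one item on the Adverse Events Summary CRF, and the window closes 30 days after the end of investigational product. The definition does not mention an event that began earlier and then worsened. The neighbouring entry builds on it: "A treatment-related AE is any treatment-emergent AE that per investigator review has a reasonable possibility of being caused by the investigational product".

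The current protocol (section 10.1.1) names the subject incidence of TEAEs as part of the primary endpoint. The SAP, which states that it follows the protocol of March 2014, still says adverse events at that point (SAP 4.1). Its adverse event summaries in 10.5.1 rest largely on the TEAE and treatment-related categories.

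The recording rules are in the protocol:

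- Section 5 starts adverse event collection at cycle 1 day 1 and adds: "Adverse Events occurring during the screening period and which are not related to study procedures will be captured as medical history".
- Section 9.2.2 requires reporting of serious events "that occur after signing of the informed consent through 30 days after the last dose of investigational product or the EOS visit", whichever is later.
- Section 9.2.1 says that an event whose severity changes is to be handled thus: "record as a single event with the worst severity on the Adverse Event Summary eCRF".
- Appendix B, on the serious event contingency form, says of the start date: "Enter date the adverse event first started; not when the event met serious criteria".
- Protocol 9.1.1 and SAP section 6 both include worsening of a pre-existing condition in the definition of an adverse event.

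**The concern.** A definition that looks only at the start of an event works if every worsening on drug gets its own start date. For conditions held in medical history that is a natural reading. For an event that already has an adverse event record, nothing tells the site to open a second record when it worsens. If the site updates the existing record, the pre-dose flag stays and the SAP rule excludes the event. The treatment-related category excludes it too, even where the investigator judges that AMG 211 caused the worsening.

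At stake is consistent counting within part of the primary endpoint. The same clinical change would count for one subject and not for another, depending only on which form held the condition at first dose. Where the worsening stays on a single worst-grade record, the record also does not show which grade occurred on drug.

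**Working it through.** The plan states no figure on this point, so the check is a comparison of the texts, followed by the arithmetic that the cohort sizes allow.

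**Step 1: can adverse event records exist before first dose?** Yes. Serious events are reported from consent (Protocol 9.2.2), and serious event reporting is listed among the screening procedures (7.2.1). The contingency form has a box for events before first dose (Appendix B). The SAP flag itself presupposes such records. For non-serious events caused by a screening procedure, such as a biopsy, the position is less clear. Section 5 does not send them to medical history, but sections 5 and 9.2.1 open non-serious collection only at or after first dose.

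**Step 2: follow each kind of pre-dose event through worsening on AMG 211.**

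| Pre-dose event | Where it sits at first dose | If it worsens on drug | Counted as a TEAE? |
|---|---|---|---|
| Pre-existing condition, or non-serious screening event unrelated to procedures | Medical history | The worsening is itself an adverse event (Protocol 9.1.1, SAP 6), with onset on treatment | Yes |
| Serious event after consent, still ongoing | Adverse event record | No rule calls for a new record; the change can stay on the existing one | No, if it stays there |
| Non-serious event caused by a screening procedure, still ongoing | Unclear; possibly an adverse event record | If recorded, the single-record instruction in 9.2.1 may be applied | No, if it is recorded and stays there |

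**Step 3: treatment-related incidence.** It is a subset of TEAEs, so whatever row 2 or row 3 loses from one is lost from the other.

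**Step 4: size.**

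- One uncounted subject in an escalation cohort of 3 to 6 (Protocol Table 3): 1/3 = 33.3 points; 1/6 = 16.7 points.
- One uncounted subject among the planned 78: 1/78 = 1.3 points.
- The rate of affected subjects is not in the documents. As an assumption only, take 2% to 5% of 78: 0.02 × 78 = 1.6 and 0.05 × 78 = 3.9, so about 2 to 4 subjects. That gives 2/78 = 2.6% and 4/78 = 5.1%.

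The last range is an upper bound for a single event type, because it needs every affected subject to have the same type of event. Incidence of any TEAE falls only for a subject who has no other TEAE.

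**Step 5: a knock-on effect.** SAP 10.5.1 omits an adverse event table when two or fewer subjects have the event. Moving from three affected subjects to two could therefore remove a table.

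**The case against.** The strongest case on the other side has four parts.

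First, the recording rules do not fit the gap exactly. The single-record instruction is in the section on non-serious events after first dose, and 9.2.2 has no equivalent for serious events. The start-date instruction in Appendix B belongs to a contingency form for restricted use, whereas the SAP reads its flag from the routine Adverse Events Summary form. This stands, and it is why the conclusion is that worsening can stay on a pre-dose record, not that it must. It does not close the gap. No rule calls for a new record, and 9.2.2 requires serious event information to agree with the Adverse Event Summary eCRF.

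Second, both documents count worsening of a pre-existing condition as an adverse event, so a site might open a new record in any case. That is a fair reading, but neither document applies it to an event already on an adverse event record.

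Third, the affected group is small. Active infection is excluded (Protocol 4.2.4), as is uncontrolled systemic disease (4.2.3). A screening biopsy is optional where archival tissue exists. All of this stands.

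Fourth, much of the safety analysis does not use the flag. DLTs are defined by occurrence in the first 28 days of treatment (Protocol 6.2.1.3). Laboratory, vital-sign and ECG changes are analysed separately. Protocol 10.4.2.1.1 tabulates fatal and serious events without a treatment-emergent limit, and SAP 10.5.1 lists every adverse event. This stands too, and it limits the effect to TEAE and treatment-related incidence.

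**Conclusion.** The gap is real and narrow. For the few events recorded as adverse events before first dose, an increase in grade or seriousness on AMG 211 can be left out of TEAE and treatment-related incidence. That does not fit the documents' own view that worsening is an adverse event.

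A reader might infer that any pre-dose condition that worsens is lost from the primary safety endpoint. The documents do not support that: most such conditions go to medical history, their worsening can return as a new event with onset on treatment, and the other components of the endpoint do not depend on the flag. Nor do they establish that serious event counts are understated. The protocol's serious event table carries no treatment-emergent restriction, and SAP 10.5.1 is mixed, using the restriction in one paragraph and not in the next.

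The frequency cannot be derived. The 17 to 33 points per cohort is simply the weight of one subject, and the 2.6 to 5.1 points overall rests on an assumed rate. The conclusion assumes that a site updates the existing record; the CRF completion guide is not among the documents, so this cannot be confirmed.

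**What to change.** In SAP section 6, define a TEAE as an adverse event with onset on or after first dose, or one with earlier onset that increases in CTCAE grade or becomes serious on or after first dose, in both cases up to and including 30 days after the end of investigational product. The treatment-related definition then follows without further change.

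In Protocol 9.2.1 and 9.2.2, state that when an event recorded before first dose worsens in this way, the worsening is entered as a new record with its own onset date. Both parts are needed: the definition sets what counts, and the separate record shows the grade reached on drug and lets the existing flag work.

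The cost is one SAP clause, one sentence in each of the two protocol sections and one CRF completion instruction. The TEAE count may be slightly higher.

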7. ANALYSIS SUBSETS

The analysis of all endpoints, unless noted otherwise, will be conducted on the Safety Analysis Set defined in Section 7.1.

7.1 Safety Analysis Set

The Safety Analysis Set will consist of all subjects that are enrolled and receive at least 1 dose of AMG 211. For the dose escalation part of the study subjects analyzed according to the initial AMG 211 dose received. For the dose expansion, subjects will be analyzed according to the dose selected for this part of the study.

7.2 Pharmacokinetic Concentration Analysis Set

The pharmacokinetic (PK) concentration analysis set will contain all subjects who received investigational product and have at least one PK sample collected.

7.3 Dose Escalation Analysis Set

The analysis of DLT will be restricted to DLT-evaluable subjects. The DLT window is 28 days for all cohorts and is independent of the length of the infusion. A subject is not DLT-evaluable if he/she drops out before completion of cycle 1 (defined as completed 90% of the planned dose in cycle 1) for reasons other than an adverse event related to the investigational product. This analysis Set will consist of all available data from all DLT-evaluable subjects, with subjects analyzed according to the treatment received initially as described for the Safety Analysis Set. Ineligible subjects may be replaced.

8. INTERIM ANALYSIS AND EARLY STOPPING GUIDELINES

Dose decision analyses are planned after every 3 to 6 DLT-evaluable subjects are enrolled throughout the dose-escalation cohorts. The DLRT considers the recommendation for subsequent doses based on the following rules:

- Based on the modified TPI Bayesian model ([Bailey et al, 2009; Neienschwander et al, 2008](#)), the next dose is the one with the highest probability of the target TPI (0.20, 0.35), but with a less than 0.25 probability of an excessive or unacceptable TPI.
- If ≥ 1 subject has a DLT at a dose level, then dose escalation cannot occur unless there are 6 or more DLT-evaluable subjects at that dose level. However, if a transient cytokine-release syndrome is reported as the DLT, but resolves within 48 hours and can be managed with prophylactic corticosteroids, the DLRT may decide to escalate the dose with the institution of prophylactic corticosteroid administration.
- The maximum allowed dose increase will be 1 dose level above the maximum of previous evaluated doses.
- Dose escalation can be achieved by evaluating a higher dose level with the same infusion duration (eg, 800 μ g/day for 14 days to 1600 μ g/day for 14 days), or by evaluating the same dose level with a prolonged infusion duration (eg, from 800 μ g/day for 14 days to 800 μ g/day for 28 days). The DLRT may also decide to explore in parallel both options mentioned above after the dose-escalation decision is made, or to prioritize one schedule. In this case, 2 TPI models may be run in parallel to obtain dose recommendations for these 2 schedules separately.
- Intermediate dose levels not pre-specified may be considered based on the optimal dose recommended by the TPI model.

The DLRT is responsible for making the decision to end dose escalation. Generally, the DLRT may consider the modeling of the dose escalation complete if 1 of the following rules is met:

- The highest planned dose level is evaluated and no DLTs occur at any dose level. In this case the maximum administered dose will be used in a dose-expansion cohort.
- The TPI Bayesian model recommends the same dose 3 times (not necessarily sequentially).
- A total of approximately 24 DLT-evaluable subjects have been enrolled.

The Amgen Medical Monitor and Amgen Global Safety Officer can make dose decisions without convening the DRLT in the following limited circumstances:

- If a cohort has at least 3 DLT-evaluable subjects and 1 subject experiences a DLT, then the Amgen Medical Monitor and Amgen Global Safety Officer may decide to expand the number of subjects treated in this cohort.
- The Amgen Medical Monitor and Amgen Global Safety Officer may decide to open the next cohort using a de-escalated dose (de-escalated from the dose level of the most recent cohort), if this de-escalated dose had been previously evaluated by the DLRT.

A safety review of dose escalation is planned after all subjects in dose escalation have had the opportunity to complete 6 months of the treatment.

